**4.3 Software**

All report outputs will be produced using SAS® version 9.4 or later in a secure and validated environment.

**4.4 Study Participants**

**4.4.1 Analysis Sets**

For purposes of analysis, analysis sets are defined as follows:

| Analysis Set                | Description   |
|------------------------------------|--|
| Enrolled Set (ES)                  | All participants who signed informed consent.  |
| Intent-to-Treat Analysis Set (ITT) | All randomized participants who received at least one dose of the study drug. Participants will be included into the analysis as randomized. This corresponds to what is referred to in ICH E9 as the Full Analysis Set. |
| Per-Protocol Set (PPS)             | All ITT participants without any major protocol deviations that could impact the primary endpoint.   |
| Safety Analysis Set (SS)           | All participants who receive at least one dose of study drug. Participants will be included into the analysis based on treatment actually received, regardless of the treatment randomized.                              |

The ITT Analysis Set will be used for all efficacy analyses and BL data analyses except participant disposition which will be shown for the ITT Analysis Set and for the Safety Analysis Set if the two analysis sets differ. All randomized participants are expected to be dosed and any exceptions will be described in the CSR. The PP set will be determined prior to database lock and will be used as a supplementary analysis of the primary endpoint.

For analyses based on the SS, participants randomized to a control treatment group who receive any dose of active OTT166 treatment will be analyzed in the corresponding OTT166 treatment group (BID or QID).

A Data Review Meeting will be arranged to identify analysis sets or data to be included/excluded from analysis, including a review/confirmation of participants with ICEs. Decisions made regarding

the exclusion of participants and/or participants data from analyses will be made prior to unmasking and will be documented and approved by OcuTerra Therapeutics, Inc.

All safety analyses will be based on the Safety Analysis Set (SS).

If a participant is stratified incorrectly, the participant will be included into the analysis as stratified per the ITT principle.

The number and percentage of participants in each analysis set will be summarized by treatment group for the ES. Inclusion in the PP set will be indicated in the listing of participant disposition for the ITT Analysis Set.

Unless otherwise specified, participant disposition, demographics, and baseline characteristics will be summarized by the randomized treatment group (i.e., vehicle control doses (5% BID, 5% QID), vehicle control combined, active OTT166 doses (5% BID, 5% QID)), and overall.

#### 4.4.2 Disposition of Participants

A clear accounting of the disposition of all participants who enter the study will be provided, from screening to study completion.

Participant disposition will be summarized for the ITT Analysis Set by treatment and overall, for:

- Number of participants randomized
- Number and percentage of participants received at least one dose of study drug
- Number and percentage of participants completed study drug
- Number and percentage of participants discontinued from study drug and primary reason for premature discontinuation
- Number and percentage of participants completed study
- Number and percentage of participants discontinued from study and primary reason for premature discontinuation

Participant disposition for participants who were screen failures (defined as participants in the Enrolled Set who were not randomized) will be summarized and will include the reason for screen failure.

By-participant listings of participant disposition details will also be provided.

#### 4.4.3 Protocol Deviations

Protocol deviations will be classified as “major” or “minor” on ongoing basis by the clinical study team and sponsor.

Major protocol deviations are defined as those deviations from the protocol likely to have an impact on the perceived efficacy and/or safety of study treatments. The impact of major protocol deviations on the efficacy results will be investigated by assessing the robustness of the study results and conclusions to the choice of analysis set, both including and excluding data potentially affected by major protocol deviations.

Major protocol deviations and any action to be taken regarding the exclusion of participants or affected data from specific analyses are defined in the project-specific Protocol Deviation Specification. Final decisions made regarding the exclusion of participants and/or participants data

from analyses will be made prior to unmasking and will be documented and approved by OcuTerra Therapeutics, Inc.

The number and percentage of participants with at least one major protocol deviation as well as major protocol deviation categories for the ITT Analysis Set by treatment and overall will be summarized. This summary will also include a summary of participants excluded from the PPS due to major protocol deviations by category.

A by-participant listing of all protocol deviations will also be provided.

#### 4.5 Demographics and Baseline Characteristics

The following demographics and baseline characteristics will be summarized on ITT Analysis Set by treatment and overall:

- Age (years)
- Gender
- Race
- Ethnicity
- Height (cm) at Baseline
- Weight (kg) at Baseline
- Body Mass Index (kg/m^2) at Baseline
- HbA1C at Baseline
- Intraocular pressure at Baseline
- DRSS steps at the Baseline Visit
- ETDRS letter score at Baseline
- Central Subfield Thickness (CST) at Baseline
- Duration of Diabetes (years) defined as time from diagnosis to randomization
- Diabetes Type (Type 1 and Type 2)
- Diagnosis of systemic hypertension

Additional demographic or baseline assessments may be added to the summary tables.

A separate summary of subgroups on ITT Analysis Set will also be provided by treatment and overall:

- Age (<65 years, ≥65 years)
- BMI (Normal [<25 kg/m^2], Overweight [≥25 to <30 kg/m^2], Obese [≥30 kg/m^2])
- HbA1C (≤7%, >7%)
- Duration of Diabetes (<median, ≥median)
- Baseline DRSS (47 or 53 or 61B)
- Presence of fluid in the central subfield at Baseline (Y/N)

By-participant listing of demographic and other baseline characteristics as well as subgroups will also be provided.

#### 4.6 Medical and Surgical History

Medical and surgical history at screening will be collected under the Medical History form of the eCRF and will be coded using the Medical Dictionary for Regulatory Activities (MedDRA) Version 24.1 or higher. Medical and surgical history will be summarized for the Safety Analysis Set by treatment and overall using system organ class (SOC) and preferred term (PT).

A by-participant listing for medical and surgical history will be provided.

#### 4.7 Prior and Concomitant Medications

Prior medication is defined as any medications that started and stopped before the first dose of study drug.

Concomitant medication is defined as any medications that started before the first dose of study drug and stops on or after the first dose of study drug, as well as any medications that started on or after the first dose of study drug.

Medication start and stop dates will be compared to the date of first dose of study drug to allow medications to be classified as either prior or concomitant. Medications starting after the End of Study, as previously defined, will not be classified or summarized.

Incomplete start and end date of the medications will be imputed as described in [Section 4.2.1](#).

Medications will be coded using the World Health Organization Drug (WHO-Drug) Global March 2022 B3G. Prior and concomitant medications will be summarized on Safety Analysis Set by treatment and overall. Participants with more than one medication in a given Anatomical Therapeutic Chemical (ATC) level 4 and preferred term will be counted only once.

By-participant listings of both prior and concomitant medications will also be provided.

#### 4.8 Rescue Therapy

Participants meeting one or all the following criteria in the study eye would qualify for rescue with anti-VEGF therapy and/or PRP laser after consultation with the Medical Monitor:

Objective Rescue Therapy Criteria:

- Worsening DRSS level to 65 or higher as determined by the central reading center
- Decrease in BCVA of  $\geq 10$  ETDRS letters from BL associated with presence of new fluid or an increase in fluid in the central subfield compared to baseline at any visit
- Decrease in BCVA of 5 to 9 ETDRS letters from BL at two consecutive visits 4 weeks apart associated with presence of new fluid or an increase in fluid in the central subfield compared to baseline
- Increase in CST of  $\geq 75$  microns from BL associated with presence of new fluid or an increase in fluid in the central subfield compared to baseline
- Development of anterior segment neovascularization (ASNV)

Subjective Rescue Therapy Criteria:

- Any other condition that, in the clinical opinion of the investigator, warrants rescue therapy after consultation with the Medical Monitor

Summary tabulations of number and percentage of participants with rescue therapy, reasons for rescue and type of rescue therapy will be provided.

A by-participant listing will be provided.

The start date of rescue therapy in the study eye will be determined by the earliest concomitant medication in the study eye with ATC4CD="SL01A" or the earliest ocular concomitant procedure confirmed by the clinical team to be rescue therapy. This will be subset on the participants who have completed the "Rescue Therapy for Ocular Diabetic Complications" eCRF.

## 4.9 Treatment Exposure and Compliance

### 4.9.1 Treatment Exposure

Exposure to study drug will be summarized using the ITT Analysis Set and also the Safety Analysis Set. The total number of doses administered, and the duration of treatment will be summarized in a summary table by treatment group and overall.

A by-participant listing of treatment exposure will be provided.

### 4.9.2 Treatment Compliance

Overall treatment compliance (%) will be calculated as:

$$\frac{\text{Total Number of Doses of Study Drug Administered}}{\text{Total Number of Doses of Study Drug Planned}} \times 100\%$$

The total number of doses of study drug administered is the actual number of drops administered. In the event a participant takes study drug after their EOS date, the total number of doses administered will not include any doses recorded after the EOS date.

The total number of doses of study drug planned is calculated based on a participant's duration in the study and the randomized treatment. A participant randomized to BID treatment will have 2 times the (date of EOS – date of first dose + 1). A participant randomized to QID treatment will have 4 times the (date of EOS – date of first dose + 1).

For participants who take rescue therapy in the study eye during the study, the total number of doses of study drug planned is calculated based on a participant's treatment duration prior to rescue and randomized treatment. A participant randomized to BID treatment will have 2 times the (date of EOT – date of first dose + 1). A participant randomized to QID treatment will have 4 times the (date of EOT – date of first dose + 1).

A summary of the treatment compliance will be provided for the ITT Analysis Set and also the Safety Analysis Set by treatment and overall.

Monthly (every 4 weeks) treatment compliance (%) will be calculated as:

$$\frac{\text{Total Number of Doses of Study Drug Administered each Month}}{\text{Total Number of Doses of Study Drug Planned for each month}} \times 100\%$$

The total number of doses of study drug planned is calculated based on a participant's duration in the study and the randomized treatment. A participant randomized to BID treatment will have 2 times the minimum of 28 or the (date of EOS – date of first dose in month + 1). A participant randomized to QID treatment will have 4 times the minimum of 28 or the (date of EOS – date of first dose in month + 1).

For participants who take rescue therapy in the study eye during the study, the total number of doses of study drug planned is calculated based on a participant's treatment duration prior to rescue and randomized treatment. A participant randomized to BID treatment will have 2 times the minimum of 28 or the (date of EOT – date of first dose in month + 1). A participant randomized to QID treatment will have 4 times the minimum of 28 or the (date of EOT – date of first dose in month + 1).

Number and percentage of participants with compliance in categories (<75%, 75-<90%, ≥90%) will be provided for overall and monthly treatment compliance.

A by-participant listing of treatment compliance will be provided.

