2.14.10.1 Permanent Discontinuation

In rare instances, it may be necessary for a participant to permanently discontinue (definitive discontinuation) study intervention. If study intervention is permanently discontinued, the participant may remain in the study for continued assessment of safety and efficacy outcomes.

Unscheduled visits may be performed as deemed appropriate by the investigator, in particular, in case of withdrawal due to an AE.

Participants *must* be withdrawn from the *study intervention* for any of the following reasons:

- If rescue therapy has been initiated
- Safety concerns for a participant by the investigator or the sponsor
- Vision threatening complication meeting rescue criteria and/or progression to worse than mild PDR with DRSS > 61
- Pregnancy (see [Section 2.17.4](#) for details)

Necessity to withdraw the participant from the study will be assessed case-by-case by the investigator in consultation with the medical monitor.

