2.14.10.2 Temporary Discontinuation

Treatment should be withheld temporarily if any of the following conditions apply:

- Occurrence of hypersensitivity after instillation of the eye drops
- Rechallenge can be considered at the discretion of the investigator in consultation with the medical monitor

The investigator may decide to temporarily discontinue treatment for other reasons if deemed appropriate for the safety and well-being of the participant. The medical monitor should be informed.

2.14.11 *Participant Discontinuation / Withdrawal from the Study*

A participant may withdraw from the study at any time at his/her own request or may be withdrawn at any time at the discretion of the investigator for safety, behavioral, or compliance reasons. This includes cases in which, in the investigator's opinion, continued participation in the study would be harmful to the participant's well-being. This is expected to be uncommon.

- At the time of discontinuing from the study, if possible, the final study visit should be conducted as early discontinuation visit, followed by safety follow-up as determined by the investigator in keeping with standard of care. See SoA for data to be collected at the time of study discontinuation and follow-up and for any further evaluations that need to be completed.
- The participant will be permanently discontinued both from the study intervention and from the study at that time.
- If the participant withdraws consent for disclosure of future information, the Sponsor may retain and continue to use any data collected before such a withdrawal of consent.

2.14.12 *Lost to Follow-up*

A participant will be considered lost to follow-up if he or she repeatedly fails to return for scheduled visits and is unable to be contacted by the study site.

The following actions must be taken if a participant fails to return to the clinic for a required study visit:

- The site must attempt to contact the participant and reschedule the missed visit as soon as possible, counsel the participant on the importance of maintaining the assigned visit schedule, and ascertain whether or not the participant wishes to and/or should continue in the study.

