|   | ICE(s) with a composite variable strategy take priority over ICEs with other strategies. And ICEs with a hypothetical strategy take priority over ICEs with treatment policy strategy.   |

A Supplemental Estimand will be defined and analyzed where the ICEs defined above will be handled using alternative strategies as follows: c and e are changed to Hypothetical strategy.

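### SAP 4.9.2 lets missed days drop out of the last, shortened month of compliance, and overall compliance scores a required stop differently depending on whether rescue followed

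*SAP*

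**What the plan says.** SAP 4.9.2 divides doses administered by doses planned. For most participants, "The total number of doses of study drug planned is calculated based on a participant's duration in the study and the randomized treatment"; on the twice-daily regimen, "A participant randomized to BID treatment will have 2 times the (date of EOS – date of first dose + 1". The four-times-daily rule is the same with a factor of 4. EOS is the participant's final available assessment after treatment (SAP 4.2), so it can fall well after the last drop.

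There is one exception. For participants rescued in the study eye, "the total number of doses of study drug planned is calculated based on a participant's treatment duration prior to rescue and randomized treatment", and the count ends at EOT. The SAP gives no date rule for EOT, and Protocol 2.15.2 treats end of treatment and end of study as one Week 24 time point.

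The monthly denominator for the twice-daily regimen is "2 times the minimum of 28 or the (date of EOS – date of first dose in month + 1", with EOT replacing EOS after rescue. Month boundaries are not tied to study days, and there is no rule for a month without a dose. Both measures are tabulated as <75%, 75–<90% and ≥90%.

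Protocol 2.14.10.1 requires study drug to stop for rescue, and also for safety concerns, pregnancy, and vision-threatening complications or progression. After a permanent stop "the participant may remain in the study for continued assessment of safety and efficacy outcomes". Protocol 2.14.10.2 adds holds: "Treatment should be withheld temporarily if any of the following conditions apply". Neither a non-rescue stop nor a hold shortens the planned-dose count.

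Protocol 2.14.4 bases expected doses on the schedule prescribed at randomization and sets non-compliance at <75%.

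**The concern.** A monthly denominator should depend on the calendar and the regimen, not on when the participant happened to take a drop. If it starts at the first drop, a participant who skips the opening days of a month can have those days removed from what was expected. A participant who takes nothing all month has no starting date, and so no defined value where 0% would be expected.

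The overall measure has a different problem. It stops counting for one kind of required stop (rescue) but keeps counting for the others if the participant stays in follow-up. Two participants with identical dosing, each of whom followed the protocol, can land in opposite compliance classes.

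What is at stake is how the compliance tables and their three categories read for the two dosing frequencies. Late lapses can be understated by month, and required stops can be reported as poor adherence overall.

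**Working it through.** The plan states no compliance figure to reproduce, so the SAP 4.9.2 formulas are applied directly.

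**Inputs.** Week 24 is Day 169 ± 7, so EOS ranges over Days 162–176 (Schedule of Activities). Assumptions: first dose on Day 1; months are Days 1–28, 29–56, …, 141–168; every prescribed dose is taken on a dosed day; the first dose in a month means the first one taken. The factor 2 or 4 then cancels.

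**Monthly, last month.** Planned days under the SAP = min(28, EOS − first dose in month + 1). Take EOS Day 169 with nothing on Days 141–154 and full twice-daily dosing from Day 155:

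- Planned: 169 − 155 + 1 = 15 days; 2 × 15 = 30 doses.
- Taken on Days 155–168: 14 × 2 = 28 doses.
- SAP: 28/30 = 93.3%. Fixed 28-day month: 28/56 = 50.0%.

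Other cases, in days:

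| EOS | First drop in month 6 | SAP | Fixed window |
|---|---|---|---|
| 162 | Day 155 | 8/8 = 100% | 8/22 = 36.4% |
| 169 | Day 148 | 21/22 = 95.5% | 21/28 = 75.0% |
| 169 | Day 162 | 7/8 = 87.5% | 7/28 = 25.0% |
| 176 | Day 155 | 14/22 = 63.6% | 14/28 = 50.0% |

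**Monthly, months 1–5.** With EOS Day 169, the latest possible first drop in month 5 is Day 140, and 169 − 140 + 1 = 30 > 28. The cap always applies and no missed day is lost: a first drop on day 15 of the month gives 14/28 = 50%.

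**Early EOS.** With EOS Day 100, month 4 (from Day 85) is the shortened one. A first drop on Day 92 gives 9/9 = 100%, against 9/16 = 56.3%.

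**Overall.** Perfect dosing to Day 85, then:

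- rescue, with EOT Day 85: 85/85 = 100%;
- leaving the study on Day 85: 85/85 = 100%;
- a required stop without rescue, followed to Day 169: 85/169 = 50.3%.

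With EOS Day 169, a required stop on or before Day 126 falls below 75% (126/169 = 74.6%; 127/169 = 75.1%). A hold with otherwise perfect dosing does so from 43 days ((169 − 43)/169 = 74.6%).

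**EOT.** A participant who stops drops on Day 57 and is rescued on Day 113 scores 57/57 = 100% if EOT is the last dose, and 57/113 = 50.4% if EOT is the rescue date.

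**The case against.** The strongest reply is that Protocol 2.14.4 itself ties expected doses to the schedule set at randomization, through Week 24. On that view, counting to EOS is intended, and a participant off drug for half the trial did receive about half the regimen, whatever the reason. This stands as a reason to keep the overall measure. It does not explain why rescue alone is exempt.

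It can also be said that tolerability is visible elsewhere. The SAP plans tables of study drug discontinuation with reasons, doses and duration of treatment, and adverse events leading to discontinuation. That is right, and it means required stops are not hidden. Nor do the documents make the compliance tables the basis for choosing a regimen; Protocol 2.1 rests dose selection on efficacy and safety.

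The first dose in the month might be meant as the first scheduled dose. If so, the last-month distortion disappears, but the text does not say so and sets no month boundaries.

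A reader might infer that monthly compliance looks too good wherever participants stop dosing. It does not. Dosing on Days 141–154 and then stopping, with EOS Day 169, gives 28/56 = 50%, which is correct. Inflation needs a late first drop in a shortened month. The overall figure still counts the gap: missing Days 141–154 gives 155/169 = 91.7%.

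**Conclusion.** The point holds for the compliance tables. In the month cut by EOS or EOT the monthly rule can overstate compliance, by 43 percentage points in the worked case (93.3% against 50.0%), and by more or less as EOS moves within its window. A month without drops has no defined value. Overall compliance gives 100% or 50.3% for the same dosing history, depending on whether the required stop was a rescue. The overall difference arises only for unrescued participants who stay in follow-up after a required stop, or who have a long hold; if EOS coincides with the stop there is none. The documents do not allow an estimate of how many participants are affected.

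A reader might infer that the efficacy estimands are compromised. The documents do not support that. In the primary estimand, compliance <75% (ICE e) is handled by treatment policy. Permanent discontinuation is ICE d, hypothetical in both estimands, so a low compliance value changes nothing for those participants. In the Supplemental Estimand, "c and e are changed to Hypothetical strategy", so a directed hold of 43 days or more with resumption could move an observed Week 24 DRSS to imputation. The only named cause of a hold is hypersensitivity, and nothing suggests holds of that length, so the effect is negligible. Any effect on the Per-Protocol Set cannot be judged, because the Protocol Deviation Specification is not among the documents.

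**What to change.** In SAP 4.9.2:

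1. Define months by study day: Days 1–28, 29–56, …, 141–168. Planned doses = frequency × number of days in that window up to EOS, or up to EOT for rescued participants. Give EOT an explicit date rule. State that days after Day 168 count in the overall measure only.
2. Score a month without drops as 0% only if it contains planned days. Show months wholly after the end of the planned-dose period as not applicable.
3. Keep the prescribed-schedule overall measure. Add a row for compliance while on treatment: end planned doses at the recorded study drug stop date for protocol-required stops (rescue, safety, pregnancy, progression), and exclude documented investigator-directed holds. Limiting this to required stops means that a participant who simply gives up dosing still counts as having missed doses.
4. Leave the definition of ICE e unchanged. A participant off drug long enough to fall below 75% did receive less than 75% of the assigned regimen.

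The cost is SAP text, some programming and one extra table row to explain. Protocol 2.14.4 already records start and stop dates, delays and missed doses. It does not show that directed holds are flagged as such, so the sponsor should confirm this first. SAP version 3.0 has no effective date yet, and SAP 4.14 allows changes until database lock.
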